7.5.5 Pregnancies

A detailed listing of all pregnancies will be provided.

7.5.6 Eastern Cooperative Oncology Group (ECOG) Performance Scores

Number of percent of subjects for each category of the ECOG performance status at each assessment time will be provided. Negative change scores indicate an improvement and positive scores indicate a decline in performance.

ECOG performance scores will also be summarized using shift table from baseline to post-baseline assessments.

7.6 Analysis of PK

PK analysis will be conducted on the PKAS.

Descriptive statistics (e.g., N, mean, standard deviation, minimum, median, maximum, coefficient of variation [CV], geometric mean, and geometric CV) will be provided for trough plasma concentrations (C_{trough}) of gilteritinib, if appropriate, by visit and time point.

7.7 Analysis of Biomarkers

The activation status of FLT3 and AXL will be summarized by dose and change from baseline at each time point.

Immune cell immunophenotyping and blast cell immunophenotyping biomarkers will be summarized by dose and change from baseline at each time point by both absolute number and percentage.

7.8 Subgroups of Interest

Not applicable for this study.

7.9 Other Analyses

Not applicable for this study.

7.10 Interim Analysis (and Early Discontinuation of the Clinical Study)

Not applicable for this study.

7.11 Handling of Missing Data, Outliers, Visit Windows, and Other Information

7.11.1 Missing Data

Every effort will be made to resolve incomplete dates for death and disease relapse. If a partial date cannot be resolved, the most conservative imputation methods will be used to complete the missing information.

For OS and EFS, missing or incomplete death date will be imputed as the earliest feasible date on or after the date of last contact as the examples shown in the table below. The date of last contact will be obtained as described in Section 6.1.2.

Incomplete Date of Death (YYYY MMM DD)	Date of Last Contact (YYYY MMM DD)	Imputed Date of Death (YYYY MMM DD)
2005 APR ??	2005 MAR 31	2005 APR 01
2005 ??? 13	2005 MAR 31	2005 APR 13
2005 ??? ??	2005 MAR 31	2005 MAR 31
???? APR ??	2005 MAR 31	2005 APR 01
???? APR 13	2005 MAR 31	2005 APR 13
???? ??? ??	2005 MAR 31	2005 MAR 31

Partial relapse dates will be imputed to the first day of the month of the missing parameter but not earlier than the last disease assessment date. A month and year must be present or the date will remain missing.

Missing or partial start and stop dates of adverse events and concomitant medication will be imputed using the following algorithm:

- Imputation rules for partial or missing stop dates:
 - If the month and year are present, then impute as the last day of that month.
 - If only the year is present, impute as December 31 of that year.
 - If the stop date is entirely missing, assume the event or medication is ongoing.
- Imputation rules for partial or missing start dates:

Start Date		Stop Date						missing
		Complete: yyyymmdd		Partial: yyyyymm		Partial: yyyy		
		< 1 st dose	≥ 1 st dose	< 1 st dose yyyyymm	≥ 1 st dose yyyyymm	< 1 st dose yyyy	≥ 1 st dose yyyy	
Partial: yyyymm	= 1 st dose yyyymm	2	1	2	1	n/a	1	1
	≠ 1 st dose yyyymm		2		2	2	2	2
Partial: yyyy	= 1 st dose yyyy	3	1	3	1	n/a	1	1
	≠ 1 st dose yyyy		3		3	3	3	3
Missing		4	1	4	1	4	1	1

1 = Impute as the date of first dose; 2 = Impute as the first of the month; 3 = Impute as January 1 of the year; 4 = Impute as January 1 of the stop year

The imputed dates will be used to determine whether an AE is/is not treatment emergent. Listings of AEs and concomitant medications will present the actual partial dates; imputed dates will not be shown.

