5.3 Efficacy Assessments

5.3.1 Bone Marrow Aspirate and Biopsy

Bone marrow samples will be collected at screening, cycle 2/day 1 and cycle 3/day 1. For subjects who do not achieve a CR, CRp or CRi, the bone marrow assessments will be repeated on day 1 of every 2 subsequent cycles. For subjects who achieve a CRc (CR, CRp or CRi), bone marrow will be repeated 1 month after the date of remission and every 3 subsequent cycles or if there is suspicion of relapse in the whole blood. Bone marrow samples are also required at the EOT Visit and as clinically indicated. If bone marrow aspirate is unobtainable due to technical difficulties such as dry tap, a tube of whole blood (ethylenediaminetetraacetic acid [EDTA]) along with bone marrow biopsy should be collected instead. Remaining bone marrow aspirate and/or whole blood samples will be used for MRD analysis and may be used for other biomarker analyses in relation to treatment outcomes [described in Section 5.7] If bone marrow aspirate is unobtainable at relapse (e.g., dry tap), a peripheral blood smear should be collected along with bone marrow biopsy lab. All samples will be sent to the central lab. Refer to the laboratory manual for additional details.

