6.1.4 Definition of Other Efficacy Variables

- CR rate - Defined as the number of subjects with CR divided by the number of subjects in the analysis population. Subjects with unknown or missing response, or who provide no information on response at the end of study will be treated as non-responders and will be included in the denominator when calculating rates.
- CRp rate, CRi rate, CRh rate, PR rate – Defined similarly as CR rate.
- Best response rate – Defined as the number of subjects with CR or CRp or CRi or PR divided by the number of subjects in the analysis population (i.e., CR+ CRp + CRi + PR). Subjects with unknown or missing response, or who provide no information on response at the end of study will be treated as non-responders and will be included in the denominator when calculating rates.
- Duration of remission – This includes duration of CRc, duration of CR, duration of CR/CRh, and duration of response (CRc + PR) by the EOT.
 - Duration of CRc – Defined as the time from the date of either first CRc until the date of documented relapse of any type for subjects who achieve CRc. Subjects who die without report of relapse are considered non-events and censored at their last relapse-free disease assessment date. Subjects who come off study for an allogeneic HSCT will be considered nonevents and censored at the time of HSCT. Other subjects who do not relapse on study are considered non-events and censored at the last relapse-free assessment date.
 - Duration of CR, and CR/CRh – Defined similarly as duration of CRc.
 - Duration of response – Defined as the time from the date of either first CRc or PR until the date of documented relapse of any type for subjects who achieve CRc or PR. Subjects who die without report of relapse are considered nonevents and censored at their last relapse-free disease assessment date. Subjects who come off study for an

allogeneic HSCT will be considered nonevents and censored at the time of HSCT.

Other subjects who do not relapse on study are considered nonevents and censored at the last relapse-free assessment date.

- Event-free survival (EFS) – The time from the date of first dose until the date of documented relapse from CR, CRp or CRi, treatment failure or death from any cause, whichever occurs first.
 - If a subject experiences relapse or death the subject is defined as having an EFS event related to either “relapse” or “death,” and the event date is the date of relapse or death.

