 - If a subject who discontinues the treatment due to treatment failure during the first 2 treatment cycles, and the subject has no previous response of CR, CRp or CRi, the subject is defined as having an EFS event and the event date is the date of first dose.
 - If a subject who discontinues the treatment due to treatment failure after the 2 treatment cycles, and the subject has no previous response of CR, CRp or CRi, the subject is defined as having an EFS event and the event date is the date of end of the 2nd treatment cycle evaluation date (i.e., cycle 3/day 1 bone marrow evaluation).
 - For a subject who is not known to have relapse or treatment failure or death, EFS is censored at the date of last relapse-free assessment date. Subject is not censored at HSCT.
- Overall survival (OS) - The time from the date of first dose until the date of death from any cause. For a subject who is not known to have died by the end-of-study follow-up, OS is censored at the date of last contact. Date of last contact is defined as the death date or the latest of the following dates: treatment discontinuation date, last dosing administration date, last disease assessment date or the last follow-up date on which the subject was known to be alive.

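### SAP 7.11.1 leaves a known relapse undated when its month or year is missing, and its earliest-date limit for other partial relapse dates can be read so as to date them late

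*SAP*

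**What the plan says.** SAP 7.11.1 covers incomplete death and relapse dates together. Sites are first asked to resolve them. Where a partial date cannot be resolved, "the most conservative imputation methods will be used to complete the missing information".

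The two kinds of date are then treated differently:

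- **Death (OS and EFS):** "missing or incomplete death date will be imputed as the earliest feasible date on or after the date of last contact". The worked table includes a row in which day, month and year are all unknown, and that row still receives a date.
- **Relapse:** "Partial relapse dates will be imputed to the first day of the month of the missing parameter", with the limit and the exception "but not earlier than the last disease assessment date. A month and year must be present or the date will remain missing".

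SAP 6.1.4 defines the endpoints that use the relapse date. For a subject not known to have relapsed, failed treatment or died, "EFS is censored at the date of last relapse-free assessment date". For duration of remission, subjects who die without a reported relapse are "censored at their last relapse-free disease assessment date", subjects who leave for an allogeneic transplant are censored at transplant, and others who do not relapse on study are "censored at the last relapse-free assessment date".

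On assessment timing, Protocol 5.3.1 adds to the scheduled marrows: "Bone marrow samples are also required at the EOT Visit and as clinically indicated".

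**The concern.** There are two separate weaknesses in the relapse rule.

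**Undated relapses.** The section undertakes to complete partial dates and then declines to do so for any relapse date lacking a month or a year. The relapse is still known to have happened, so the subject is an event with no event time. The Kaplan-Meier code in SAP 7.4.2 needs a time for each record. Unless the plan supplies one, the subject either falls out of the analysis or is handled by a choice made during programming of an open-label study.

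**The earliest-date limit.** Where SAP 6.1.4 means an assessment at which the subject was still in remission, it says relapse-free. In SAP 7.11.1 that qualifier is absent. The same unqualified term appears in SAP 6.1.4 as a component of the date of last contact, where it covers any assessment whatever its result. A programmer could reasonably reuse that variable. If an assessment follows the relapse, the limit would then push the relapse date forward to it.

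At stake are EFS and duration of remission, both secondary endpoints. Duration is estimated in responders only, in a trial of at most 61 subjects, so a few events can matter to a median.

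**Working it through.** **1. The plan's own figures.** SAP 7.11.1 gives a worked table for death dates only, with last contact on 31 Mar 2005. The rule is the earliest calendar date on or after last contact that agrees with the known parts. All six rows reproduce. The relapse rule was then applied to the same six patterns, with 31 Mar 2005 as the limit:

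| Known parts | Death rule | Relapse rule |
|---|---|---|
| 2005 APR ?? | 1 Apr 2005 | 1 Apr 2005 |
| 2005 ??? 13 | 13 Apr 2005 | missing |
| 2005 ??? ?? | 31 Mar 2005 | missing |
| ???? APR ?? | 1 Apr 2005 | missing |
| ???? APR 13 | 13 Apr 2005 | missing |
| ???? ??? ?? | 31 Mar 2005 | missing |

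The death rule completes 6 of 6 and the relapse rule 1 of 6. Of the five left missing, four are partial dates and one is wholly missing.

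**2. Whether another rule covers the five.**

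- EFS censoring applies only to subjects not known to have relapsed, so it excludes them.
- Duration censoring applies to death without reported relapse, allogeneic transplant, and no relapse on study. A known relapse fits none of these unless a transplant intervenes.

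The possible outcomes differ in direction:

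- Dropping the subject moves the curve either way, depending on that subject's unknown time.
- Censoring the relapse, or counting a later death as the EFS event, lengthens the estimate.

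The SAP specifies none of these.

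**3. The earliest-date limit.** With month and year known, imputed date = max(first of recorded month, limit). Read literally, the limit is the last assessment of any result. On the other reading it is the last relapse-free assessment. Days late = literal date minus relapse-free date.

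*Assumed example A.* Last relapse-free marrow 10 Feb 2021, relapse recorded as March 2021, end-of-treatment marrow 20 Apr 2021.

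- Literal: max(1 Mar, 20 Apr) = 20 Apr.
- Relapse-free: max(1 Mar, 10 Feb) = 1 Mar.
- Difference: 31 + 19 = 50 days, and the literal date lies outside the recorded month.

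*Assumed example B.* First dose 3 Jan 2005, last relapse-free marrow 28 Mar 2005, relapse recorded as April 2005. The relapse-free reading always gives 1 Apr. EFS day = date minus first dose + 1, so 1 Apr is day 89.

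| Last assessment of any result | Literal date | Days late | EFS day |
|---|---|---|---|
| 28 Mar (none later) | 1 Apr | 0 | 89 |
| 20 Apr | 20 Apr | 19 | 108 |
| 16 May | 16 May | 45 | 134 |
| 13 Jun | 13 Jun | 73 | 162 |

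The last two rows fall outside the recorded month. The dates are illustrations; the documents give none.

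**4. Whether a later assessment can occur.** It can. A marrow is required at end of treatment. SAP 6.1.3 allows relapse to be declared on peripheral blasts or extramedullary disease, without a marrow. Under Protocol 6.1, withdrawal for recurrence also needs the investigator's view that benefit has been lost, so treatment and marrows may continue.

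**5. Number affected.** The documents give no figure. Assuming 20 relapses with 0 to 10% incompletely dated, it is 0 to 2 events. Both inputs are assumptions.

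**The case against.** The limit on an event date is naturally read as the last assessment before that event. For a CRc responder that assessment is normally relapse-free, and nothing shifts. The literal reading can place a relapse outside its recorded month, which defeats the first-of-month instruction in the same sentence and so can hardly be intended. This stands as far as it goes: the limit is ambiguous rather than plainly wrong, and a reader who inferred that relapses will routinely be dated late would go beyond the text.

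The affected case is also narrow. On-treatment relapses come mainly from marrows and blood counts and would normally carry a full date. If the end-of-treatment marrow itself documents the relapse, using its date is arguably not an error. Incomplete dates are likelier from telephone follow-up, but no marrow is scheduled after end of treatment, so there the limit causes no delay. That setting is, however, where a month may be unknown, so the missing-date gap remains.

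The conservative undertaking speaks of partial dates, and a wholly missing relapse date is not partial. That is fair, and it confines the direct contradiction to the four partial patterns in the table. The absence of any rule for a known, undated relapse applies to all five.

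Finally, EFS and duration of remission are summarised descriptively, with no hypothesis test. That is right, and it sets the severity.

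**Conclusion.** The point holds as a minor correction. The missing-date sentence is the firmer half: it conflicts with the section's own principle and leaves a known relapse without an event time or a rule. The earliest-date limit is ambiguous. Read literally, it delays a relapse only when month and year are known and a later assessment that is not relapse-free follows the first of that month. The delay is 0 otherwise, and 19 to 73 days across the assumed examples in which it occurs.

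Two stronger inferences are not supported:

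- **That both features lengthen EFS and duration.** The literal limit can only move a relapse later, but for undated relapses the direction depends on a handling rule the SAP does not state.
- **That the shift is bounded at about 84 days (3 cycles of 28 days).** The three-cycle marrow interval in Protocol 5.3.1 applies to subjects in remission, with an extra marrow on suspicion of relapse. It does not govern assessments after relapse, and the literal limit has no such ceiling.

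The number of subjects affected is unknown and probably small. The primary CRc rate, the two-stage decision and OS do not use relapse dates and are unaffected.

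**What to change.** Replace the two relapse-date sentences in SAP 7.11.1 with a rule to this effect:

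- If month and year are known, impute the first day of that month. If only the year is known, impute 1 January.
- The imputed date is not earlier than the day after the last relapse-free disease assessment before the relapse, and not later than the first assessment showing relapse.
- If the date is otherwise unknown, use the day after that last relapse-free assessment.
- Delete the sentence that leaves the date missing.

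In example A this gives max(1 Mar, 11 Feb) = 1 Mar 2021. In example B, with the last relapse-free marrow on 28 Mar 2005, all six patterns of known parts receive a date: 1 Apr for the first and 29 Mar for the other five.

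The day-after convention is a choice; the death rule uses on or after. What matters is that one convention is fixed in advance. A sensitivity analysis of the imputed relapses would show whether it matters.

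The cost is a short rewording, which the SAP permits before hard lock, and no new data. EFS and duration estimates may become slightly less favourable.

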7.11.2 Outliers

All values will be included in the analyses.

7.11.3 Visit Windows

Visit windows are allowed for certain visits per the schedule of assessments. Subject data will not be excluded from analyses due to the subject's failure to comply with the visit schedule. The visit windows for assessments are described in the following table.

CRF visit	Visit Window
Screening	D-14 to D-1
Cycle 1 Day 1	No Window
Cycle 1 Day 8	C1D8± 1
Cycle 1 Day 15	No Window
Cycle 2 Day 1	No Window
Cycle 2 Day 15	No Window
Cycle X Day 1	No Window
Cycle X Day 15	No Window
End of Treatment Visit	Last dose date + 7

Scheduled visit will be calculated using number of days relative to the first dose based on 28-day cycles. In the case of multiple observations at a specific visit, the observation which is closest to the target date will be used. If the observations have the same distance to the target visit, the latest one will be used.

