- c. Telephone contact every 3 months, from the date of the 30-day follow-up visit additional contacts may be made to support key analyses. Subjects will be followed for up to 3 years after the 30-day follow-up visit.
- d. Height measurement performed only at screening. Weight measurement should be performed at screening and at day 1 of each cycle.
- e. Subject has an ECOG performance status ≤ 2 at screening to be eligible to enroll in study.
- f. ECG assessment will be evaluated at screening, predose on cycle 1 days 1, 8 and 15, and days 1 and 15 of each subsequent visit and at EOT. Predose assessments should be taken within 1 hour before drug administration. The 12-lead ECGs will be recorded in triplicate (3 separate ECGs with 10 min resting prior to first ECG and at least 5 min apart per time point), and transmitted electronically for central reading. The mean QTcF of the triplicate ECG tracings based on central reading will be used for all treatment decisions. If the mean triplicate QTcF is > 500 ms at any time point, the ECG will be repeated (within 2 h if identified on machine read or as soon as possible if identified by central read). See [Section 5.4.4] for further guidance on treatment decision.
- g. WOCBP must have a negative serum or urine pregnancy test (minimum sensitivity 25 IU/L or equivalent units of human chorionic gonadotropin).
- h. Subjects may be screened and enrolled from local labs only. However, clinical laboratory samples must also be submitted for central read. Laboratory tests and/or ECGs can be repeated during the screening period. In the event that the central laboratory results received after randomization are not within eligibility parameters, the subject will still be considered eligible, if local labs met the eligibility criteria, and will not be considered a protocol deviation. Local laboratory results that support eligibility and dosing decisions must be entered into the clinical database. If local laboratory is to be used to support dosing decisions, local laboratory tests will include complete blood count with differential and clinical chemistries (e.g., potassium levels, magnesium levels, glucose, serum creatinine, alanine aminotransferase and aspartate aminotransferase). Additional assessments may be done centrally or locally to monitor AEs or as required by dose modification requirements.

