5.4.4 Electrocardiogram

A 12-lead ECG will be performed during the screening period, predose of cycle 1/day 1, cycle 1/day 8, cycle 1/day 15, day 1 of each subsequent cycle, day 15 of each subsequent cycle and at the EOT visit. Predose assessments should be taken within 1 hour before gilteritinib alone or in combination with atezolizumab administration on the days when the combination is given. The 12-lead ECGs will be recorded in triplicate (3 separate ECGs, 10 minutes resting prior to first ECG and at least 5 minutes apart per time point) and transmitted electronically for central reading. The mean QTcF of the triplicate ECG tracings based on central reading will be used for all treatment interruption and reduction decisions.

If the mean triplicate QTcF is > 500 ms at any time point, on local read, the ECG will be repeated (within 2 hours if identified on machine read or as soon as possible if identified from central read). Cardiology consult will be obtained as medically indicated. If QTcF > 500 ms is confirmed, then the investigator will interrupt and reduce gilteritinib per the interruption or reduction guidelines in [Section 5.1.2 Reduction in Dose of the Study Drug(s)].

ECGs are to be performed prior to obtaining the time-matched pharmacokinetic sample, therefore, the ECGs must be started at least 10 to 15 minutes before the pharmacokinetic draw. Whenever a study procedure coincides with the scheduled time point for an ECG

triplicate, the study activities will ideally be undertaken in a fixed sequence: ECG triplicate first, vital signs (blood pressure and heart rate) second and any type of blood draw as the last assessment. This order of events is not mandatory and can be changed if required in order to accommodate pharmacokinetic time points.

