7.5.2 Clinical Laboratory Evaluation

The baseline visit is the last measurement taken prior to initial study drug administration.

Quantitative clinical laboratory variables, i.e., hematology, serum chemistry, coagulation and urinalysis will be summarized using mean, standard deviation, minimum, maximum and median at each visit. Additionally, change from baseline will be calculated as the

post-baseline value minus the baseline value and summarized in the same way. Each laboratory result will be classified as low (L), normal (N), or high (H) at each visit according to the laboratory supplied reference ranges.

The number and percentage of subjects below and above reference range will be summarized at each visit.

Frequency tabulations of qualitative clinical laboratory variables (urinalysis) will be presented at each visit.

Clinically significant abnormalities in laboratory values will be presented.

For hematology and chemistry two types of shift tables will be presented:

- Shift tables of changes based on reference range defined category (low, normal, high) from baseline to each visit as well as worst finding during the treatment period, and
- Summary shifts of changes based on reference range defined category from baseline to each visit as well as worst finding during the treatment period (shift from high or normal to low, shift from low or normal to high, categorized increase [shift from low to normal or from normal to high], categorized no change [value stays in the same reference range], categorized decrease [shift from high to normal or from normal to low]).

Laboratory results will also be graded using NCI-CTCAE v5.0, where possible. Parameters that have criteria available for both low and high values, i.e., hypo- and hyper-, will be summarized for both criteria. The same subject can be counted for both values if the subject has different laboratory values meeting each criterion. NCI-CTCAE grade of laboratory evaluations will be summarized by number and percentage of subjects for each visit. Shift tables of NCI-CTCAE grade change from baseline to worst post-baseline grade will also be presented.

Laboratory results based on central assessment will be used for summaries as described above. Laboratory results based on local assessment and bone marrow results will be listed only. The laboratory results may be displayed in figures.

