7.5.2.1 Liver Enzymes and Total Bilirubin

The following potentially clinically significant criteria in liver function tests for Alkaline Phosphatase (ALP), Alanine Transaminase (ALT), total bilirubin, Aspartate Transaminase (AST) and their combination are defined. The subject's highest value during the study will be used.

Parameter	Criteria
ALT	> 3xULN > 5xULN > 8xULN
AST	> 3xULN > 5xULN > 8xULN
ALT or AST	> 3xULN
Total Bilirubin	> 2xULN
ALP	> 1.5xULN
ALT and/or AST AND Total Bilirubin(*)	(ALT and/or AST > 3xULN) and total bilirubin > 2xULN

(*) Combination of values measured within same sample

The number and percentage of subjects with potentially clinically significant values in liver enzymes and total bilirubin will be presented.

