7.5.4 Electrocardiograms (ECGs)

12-lead ECGs will be recorded in triplicate at the scheduled time points. Each ECG tracing will be taken at least 5 minutes apart and transmitted electronically to central reading. The mean of the triplicate ECGs from central read should be used for all final treatment decisions, AE reporting and in the summary for analysis at each visit.

ECG variables including changes from baseline will be summarized using mean, standard deviation, minimum, maximum and median at each visit.

Number and percentage of subjects with normal and abnormal results as assessed by central read for the overall interpretation will be tabulated at each visit. A shift analysis table showing shift in overall ECG interpretation from baseline to each time point will be provided. The worst of the three overall ECG interpretations will be used as the time-specific overall ECG interpretation for a subject.

The QT interval corrected for heart rate by Fridericia’s formula, QTcF, is defined as: $QTc(F) = QT/(RR)^{0.33}$, where RR interval is inversely proportional to heart rate (approximately $RR = 60/\text{heart rate}$).

The QTcF interval will be summarized using frequency tables at each visit for values of clinical importance using the range criteria below.

	QTc Interval Criteria Value (msec)	
	Cumulative Category	Interval Category
Normal	≤ 450	≤ 450
Borderline	> 450	> 450 to ≤ 480
Prolonged	> 480	> 480 to ≤ 500
Clinically significant	> 500	> 500

The QTcF interval will also be summarized by the frequencies of subjects with a change from baseline of clinical importance using the criteria identified below. These summaries will be provided at each visit.

Variable	Change from Baseline	
	Cumulative Category	Interval Category
QTc Interval (msec)	<0	<0
	≥ 0	≥ 0 to ≤ 30
	> 30	> 30 to ≤ 60
	> 60	> 60

Number and percentage of subjects with 12 lead ECG abnormalities at each visit as well as number and percentage of subjects whose 12 lead ECG reading shift from baseline to each visit will be tabulated.

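### QTcF means above 500 ms that a same-day repeat does not confirm drop out of the SAP's by-visit tables, and the worst-grade laboratory table omits local results

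*SAP*

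**What the plan says.** **Selection rule.** SAP 7.11.3 places visits by days from first dose on 28-day cycles and takes one value per visit: "In the case of multiple observations at a specific visit, the observation which is closest to the target date will be used". For ties it adds: "If the observations have the same distance to the target visit, the latest one will be used".

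**ECG.** SAP 7.5.4 states: "The QTcF interval will be summarized using frequency tables at each visit for values of clinical importance using the range criteria below". The change-from-baseline categories are also by visit. The value entered is the mean of the centrally read triplicate. A worst-of-three rule exists, but it covers only the normal/abnormal interpretation within one triplicate. No maximum post-baseline QTcF is specified. Under Protocol 5.4.4, when a triplicate mean exceeds 500 ms, "the ECG will be repeated (within 2 hours if identified on machine read"; if the value is found on central read, the repeat is to follow as soon as possible. Dose action is tied to a confirmed value above 500 ms.

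**Laboratory.** SAP 7.5.2 bases its summaries, including the shift to worst post-baseline CTCAE grade, on central results. It then says: "Laboratory results based on local assessment and bone marrow results will be listed only". Protocol Table 1 footnote h allows more: "Additional assessments may be done centrally or locally to monitor AEs or as required by dose modification requirements". It also requires local results that support dosing decisions to be in the database. In a crisis, Protocol Appendix 12.10 Table 8 accepts samples taken at a local facility when the clinic visit is missed. For the liver criteria, SAP 7.5.2.1 says "The subject's highest value during the study will be used" and does not say which laboratory's values count.

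**The concern.** Safety and tolerability is a primary objective. Protocol 1.3.1 lists QT prolongation and ALT and AST increases among the expected reactions to gilteritinib, and hepatitis is an adverse event of special interest for atezolizumab. A reader will go to the above-500 ms row, the worst-grade shift and the combined ALT/AST and bilirubin row for these signals.

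QTcF is out of line with the rest of the SAP. Vital signs use the highest value, liver tests the highest value during the study, and laboratory grades the worst post-baseline grade. QTcF alone has only by-visit tables. There, a first central mean above 500 ms can be replaced by the repeat taken because it looked high. With at most 61 subjects, one or two misplaced subjects visibly change such a row.

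The laboratory tables do use worst values, but from a source that may not hold the worst value, because AE monitoring and dose-modification testing may be local.

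**Working it through.** The plan states no figure on this point, so there is nothing to reproduce. The check applies the rules as written.

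**1. QTcF selection.** Inputs: SAP 7.11.3 (closest day to target; on a tie, the latest) and SAP 7.5.4 (cut at 500 ms, by visit). Distance is taken in days, as 7.11.3 implies, so two triplicates on one day tie. The values below are illustrative central means for cycle 2/day 1 (study day 29).

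| Sequence | By-visit table uses | Category | Maximum would give |
|---|---|---|---|
| 512, then 488 the same day | 488 | >480 to ≤500 | 512, >500 |
| 512, then 508 the same day | 508 | >500 | 512, >500 |
| 512, then 488 three days later | 512 | >500 | 512, >500 |

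Only the first sequence changes category. In the third, the first reading is 0 days from target and the repeat is 3, so the first is kept.

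**2. How often a repeat would fail to confirm.** Assumptions not in the documents: the first and repeat triplicate means are independent given a true QTcF μ, the within-subject SD is 5 to 12 ms, and the repeat is on the same day. Then P(repeat ≤ 500) = Φ((500 − μ)/SD).

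- μ = 490: Φ(10/12) to Φ(10/5) = 80% to 98%
- μ = 500: Φ(0) = 50%
- μ = 510: Φ(−10/5) to Φ(−10/12) = 2% to 20%

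Most of the loss is therefore in subjects whose true value is near or below the limit.

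**3. Subjects lost from the above-500 row.** Further assumptions not in the documents: a proportion p of 61 subjects has a central mean above 500 ms at a scheduled visit, a fraction u of those has a same-day repeat at or below 500 ms, and each has one such event. The expected loss is 61·p·u, and P(at least one lost) = 1 − (1 − p·u)^61.

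| p | u | Expected lost | P(at least one) |
|---|---|---|---|
| 2% | 25% | 0.3 | 26% |
| 5% | 50% | 1.5 | 79% |
| 10% | 75% | 4.6 | 99% |

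**4. Laboratory data.** No rate of local-only testing is given, so the passages are set side by side.

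- Worst CTCAE grade shift (SAP 7.5.2): central only. A local value changes the true worst grade if it is worse than every central value or has no central counterpart, and in either case the table does not see it.
- Liver criteria (SAP 7.5.2.1): the central-only sentence in 7.5.2 refers to summaries described above it, and the liver table comes after it. The listing-only sentence, read generally, excludes local values; the highest-value sentence, read alone, includes them. Both readings are open.
- Combined ALT/AST and bilirubin row: both values must come from the same sample. If the only qualifying sample is local, the listing-only reading misses the subject.
- Opportunity: after cycle 1, scheduled samples fall on days 1 and 15 of a 28-day cycle, about 14 days apart. Protocol Appendix 12.5 asks for a retest within 72 hours, and for confirmed moderate abnormalities 2 to 3 times weekly, then weekly or less once they stabilise. A peak can fall between scheduled samples.

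**The case against.** The strongest reply is that the readings that matter for action survive. A reader might infer that the tables drop the QTcF values that trigger dose changes. They do not. Protocol 5.4.4 ties dose action to confirmation, and a confirming same-day repeat is itself above 500 ms and is the value kept. The displaced reading prompts a repeat ECG, not a dose change. This stands.

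Nor does the rule always push the table down. A repeat can be higher than the first reading, which raises the change-from-baseline entry. The 2-hour repeat follows a machine read while the tables use central reads, so a value above 500 ms on the machine may never have been above 500 ms centrally. This also stands: the loss needs a central mean above 500 ms and a same-day central repeat at or below it.

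On the laboratory side, a reader might multiply 2 to 3 tests a week by 2 weeks and conclude that 4 to 6 samples go missing. That is a ceiling. It assumes every retest is local and ignores the step down to weekly or less, and it counts samples, not subjects. Appendix 12.5 does not call for local testing and describes central-laboratory alerts. If the first abnormality was central, the subject is already in the first-threshold row. A reader might also take exclusion from the liver table as settled; the text leaves it ambiguous.

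Other outputs carry part of the signal: local results are listed, clinically significant findings not due to the disease are reported as adverse events, a confirmed Hy's law case is a DLT, and potential cases are adverse events of special interest. These soften the gap but do not replace a subject-level maximum. The statement in SAP 7.11.2 that all values are included does not close it either. It is an outlier rule, and it sits awkwardly with one value per visit.

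**Conclusion.** The point holds in a limited form.

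- **QTcF.** Applied as written, SAP 7.11.3 and 7.5.4 remove from the above-500 ms row a central triplicate mean above 500 ms that a same-day repeat does not confirm, and no maximum table restores it. Confirmed excursions and those repeated on a later day stay. This rests on distance being measured in days.
- **Size for QTcF.** It cannot be derived from the documents. The 0.3 to 4.6 of 61 subjects is a range over assumed rates, not an estimate.
- **Laboratory.** The worst CTCAE grade shift omits local values that are worse than the central ones or have none beside them. The source for the liver table is unclear. The size cannot be quantified.

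The SAP should be changed: the outputs concern expected drug reactions under a primary safety objective, and the remedy is small.

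**What to change.** 1. In SAP 7.5.4, add per-subject tables of maximum post-baseline QTcF and maximum change from baseline. Take them over all centrally read post-baseline triplicate means, including repeat and unscheduled ECGs, with the existing category limits. In SAP 7.11.3, state that the one-value-per-visit rule applies to by-visit summaries only, and reconcile this with 7.11.2.
2. In SAP 7.5.2 and 7.5.2.1, derive the worst CTCAE grade shift and the liver criteria from central and local results together, each against its own laboratory's limits. At minimum, use local results where no central result exists. Keep by-visit summaries on central data.

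The cost is SAP wording and a few extra tables, with no new assessments. The ECG data are already collected, and the SAP already plans to list local laboratory results. The one downside is that local results carry different reference ranges and must be standardised to multiples of their own ULN before they are pooled.
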